The hypothesis for this study is that human lung toxicity will decrease for smokers substituting e-cigs for smoking, but the effect will be less for the e-cig devices compared to quitting with NRT. The effects will be lessened for e-cigs without nicotine because of the anti-inflammatory effects of nicotine. This study is highly significant because it will provide direct evidence for the effects of e-cigs on inflammatory pathways in the human lung among smokers, and identify the magnitude of reduction (if any), facilitating FDA decision making for product designs. We will have scientific rigor by using a randomized group assignment and laboratory quality control measures. The data will be useful for future studies using the SREC and commercially available e-cigs differing in design, voltage and constituents, and studies of longer duration. This study is innovative because it will provide experimental evidence in humans for target organ effects, has a focus on smokers, and incorporates inflammation with untargeted metabolomic and gene expression data allowing for a complementary and comprehensive approach for data integration (e.g., does the combination of several 'omics types better distinguish treatment effects). Notably, this application responds to PAR-17-156: "Evaluating the NIDA Standardized Research E-Cigarette in Risk Reduction and Related Studies", and the NIDA research agenda by directly addressing the PAR's goals for assessing the SREC and pulmonary research. The Specific Aim for this two year project is:

1. To assess inflammatory changes over 10 weeks (8 weeks experimental condition) for lung and urine biomarkers in smokers in a clinical trial where subjects are randomized to continued use (n=32), complete switching to the nicotine SREC (n=32), complete switching to placebo SREC (n=32), or complete switching to NRT (n=32).

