Proteomics analyses: Ultraperformance liquid chromatography-tandem mass spectrometry (UPLC-MS/MS) is a well-established method to survey the proteins at a global level from a biological sample of interest. Label-free quantification and tandem mass spectrometry will be employed to assess and quantify the global proteomic profiles. Proteins from epithelial cells will be digested into peptides and separated by reversed phase chromatography prior to infusion into a Q-Exactive-HF electrospray tandem mass spectrometer. Using this approach, approximately 5,000 proteins can be quantified in each patient sample. For the data analysis, the relative abundance of the proteins will be compared in e-cigarette samples versus control samples. Individual peptides will be identified by their tandem mass spectra and correlated with their associated proteins. The abundance ratios of the peptides enable relative quantification of the associated proteins. These values can then be used to determine proteins that are differentially regulated. Ingenuity Pathway Analysis, a software designed to map the proteins to known signaling pathways, will also be used to gain a better understanding of the changes that e-cigarette use has on cellular functions.

Nitric oxide: Fractional exhaled nitric oxide (FeNO) is a validated marker of lower airway inflammation that is simple to assess, non-invasive and reproducible [166, 167]. It is used for the diagnosis and treatment of asthma in children [168-172]. Nitric oxide (NO) is present in cigarette smoke and synthesized in the lung by NO synthase (NOS) and the oxidation of L-arginine to L-citrulline [32]. The inducible NOS (iNOS) is transcriptionally regulated by pro-inflammatory cytokines in epithelial cells and macrophages in the airways [173]. FeNO is decreased by almost 50% in smokers [174-177]. The reduction in FeNO also is thought to be related to nitric oxide synthase inhibition due to cigarette smoke carbon monoxide and/or oxygen free radicals [175, 178]. Reduced FeNO has been reported to be significantly associated with neutrophilic inflammation [179]. It has been reported that FeNO reverts back to non-smoking controls levels after smokers quit for 4 or 6 weeks [69, 71]. In this application, FeNO will be used as a non-invasive marker for the reduction in inflammatory related to e-cig use.

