There has been some toxicology testing for e-cig liquids and aerosols, but these are limited and the relationship to human disease risk is unclear [8, 206, 207]. Existing studies suggest that the toxicological responses are qualitatively similar to smoking, e.g., exposing cell lines and culture to the aerosols induce an effect on inflammation [208, 209], disruption to epithelia barriers [210], oxidative stress [211], cytotoxicity [212], neutrophil inflammatory response [213] and DNA damage [114, 115]. However, the magnitude of effect is low compared to cigarette smoke. Aerosols were not found to be mutagenic [214]. Normal human bronchial epithelial (NHBE) cells exposed to e-cig aerosols, with or without nicotine, increase IL-6 and IL-8 cytokine levels [215]. Another study reported a change in the gene expression pattern of NHBE cells with silenced p53 and activated KRAS when exposed to e-cig aerosol [181]. Separately, e-cig liquid was assessed in NHBE cells in parallel with a knock-out mouse model; there were increased rates of infection, inflammatory markers and altered gene expression [216]. Metals present in e-cig aerosol are capable of causing cell injury and inflammatory cytokine induction, e.g., in human lung fibroblasts [113]. There have been some studies of gene expression in cultured human bronchial epithelial cells showing changes in profiles that are much less than smoking but clearly distinctive [217]. The pathways that have been implicated in these studies include phospholipid and fatty acid triacylglycerol metabolism, with enrichment of cell cycle associated functions (e.g., cell cycle checkpoint regulation, control of mitosis) and immune system function.

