**The Effects of a Standardized Research E-Cigarette on the Human Lung:
A Clinical Trial with Bronchoscopic Biomarkers**

NCT03691350

Statistical Analysis Plan, 09/19/22

SREC SAP

The Specific Aim for this two year project is:

To assess inflammatory changes over 10 weeks (8 weeks experimental condition) for lung and urine biomarkers in smokers in a clinical trial where smokers are randomized to: continued use (n=32), complete switching to the nicotine standardized research electronic cigarette (SREC) (n=32), complete switching to the placebo SREC (n=32), or complete switching to nicotine replacement therapy (NRT) (n=32).

- 1) We will enroll 128 subjects (32 per group). For power calculations, we will use a conservatively planned 66% retention rate at 5 weeks, knowing that we have a 100% retention for never smokers receiving serial bronchoscopies. Thus, the final sample size will be 21 subjects per group (n=84). Although we expect a higher retention rate, we assume 66% to ensure that we have the minimal numbers required to reach meaningful conclusions. Since follow-up samples would not be obtained from subjects that do not finish the treatment protocol, and these samples (inflammation/omics) are our primary outcomes, we cannot use an 'intent to treat' strategy since dropouts will have missing outcome data for any analyses including follow-up measurements (the primary Aim). In light of this, we will compare dropout rates between arms and with demographic/clinical to ensure that the analyses results are not biased by unbalanced dropouts. We will also test for differences in baseline molecular measurements between subjects that dropout after baseline samples are taken vs. subjects that complete the protocol. While we will make every effort to minimize the missing data for this study, missing data can arise due to various reasons. Violation of missing completely at random (MCAR) will be checked by evaluating whether any covariates are associated with missing data. If so, these covariates will be subsequently included and controlled for in the GL(M)M models. In addition, sensitivity analyses will also be conducted using results from multiple imputation.

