- 2) Descriptive statistics and clustering (e.g., principal components analysis [PCA]), will be performed for all biomarker data measured at the different visits. Baseline data (1st bronchoscopy) will then be compared between the four groups (3 conditions and control) using a one-way analysis of variance (ANOVA). The non-parametric Kruskal-Wallis test (continuous or ordinal variables) or the chi-square test (categorical variables) will be applied when the normality assumption of the data is not met. We will compare controls to complete substitution with the SREC (with and without nicotine) or NRT. Generalized linear models (GLM) will be employed with measurement (cell count, gene expression, etc.) as the dependent variable, a covariable for baseline measure, and a main effect of arm. Other relevant variables that are associated with the biomarker results, e.g., baseline smoking, Fagerstrom Test for Nicotine Dependence (FTND), or gender will also be included in our models as they are potential confounders. We also will assess batch effects and include batch as a co-variable in the model (all samples will be analyzed at the same time, except for cell counts). We plan to use baseline molecular measurement as a covariable rather than

modeling the change between baseline and follow-up because the former is more powerful [1]. Given the large dynamic range of the cell count and the 'omics data, we will initially consider a normal distribution. If the data are determined to deviate from normality, we will log-transform the data or assume a non-normal distribution of residuals (such as Poisson) for the GLM. Urine propylene glycol (PG) will be measured at the 2nd bronchoscopy visit and compared to baseline to verify e-cig use. As an exploratory analysis, urinary PG will be used as the exposure predictor variable assessing the biomarker results as dependent variables. Urine anatabine, urine anabasine and nicotelline will be used to confirm complete substitution or a predictor variable for smoking reduction. The cotinine level will be used as a surrogate for smoking reduction.

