Understanding the epigenomic/genomic/proteomic/environment context and regulation of metabolic phenotypes will expand our knowledge of the effects of e-cig on lung biology, and could contribute to finding successful interventions, including accurate predictions of e-cig related adverse effects. Typical omics integration methods include logistic regression or correlations among omics measurements (when measured in the same samples), intersection of gene/protein/metabolite lists (when measured in different samples), or further downstream integration by assessing alterations in pathways. Because our omics measurements will be made in the same sample, we will be able to directly assess relationships between our molecular data through regression or correlation analyses. Of note, typical regression/correlation approaches are not appropriate for low sample numbers, and they do not readily adjust for differences in sample size between phenotype groups or for potential confounders. Another approach, which we propose here, is to directly test whether associations between miRNA or gene or cytokine and metabolite levels are specific to a group assignment. To test this, we will apply a novel linear model approach recently developed by [name] for these types of analysis: $m = g + t + g:t$, where m are metabolite abundances, g are miRNA or gene or cytokine levels, t is treatment group (e.g., SREC vs. continued smoking), and g:t is the interaction between miRNA or gene or cytokine level and treatment group. A statistically significant g:t interaction p-value would indicate that gene (or miRNA or cytokine):metabolite relationships are present in one treatment group and not the

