other. Pathway enrichment analysis of associated miRNA, genes, cytokines, and metabolites (resulting from the linear models) will be performed in Ingenuity Pathway Analysis to pinpoint altered pathways and better understand how the epigenomic/genomic/proteomic/environment affects metabolic phenotypes associated with e-cig usage. Furthermore, miRNA, genes, cytokines, and metabolites involved in treatment-specific associations will be used to predict treatment group, in an effort to produce an e-cig inflammation signature. Ten-fold cross-validations of various linear-based and non-linear based machine learning methods will be tried (e.g., Random forests, naïve Bayes, Lasso) and the resulting specificity and sensitivity will be assessed to select the best performing model. Of note, the cross-validation will help ensure that the predictive models are not overfit and could be predictive on new validation data. The contribution of input molecular measurements (gene, cytokines, miRNAs, metabolites) to the model will be assessed to define the minimal set of features that yield the optimal cross-validated models.

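### The SAP does not say which groups define the e-cig inflammation signature, and its only example contrast cannot separate starting aerosol from stopping cigarettes

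*SAP*

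**What the plan says.** SAP item 2 and Protocol 4.g.i (Data Analysis Plan) describe the same three steps.

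- **Model.** m = g + t + g:t, where m is a metabolite, g a miRNA, gene or cytokine level, and "t is treatment group (e.g., SREC vs. continued smoking").
- **Selection.** "A statistically significant g:t interaction p-value would indicate that gene (or miRNA or cytokine):metabolite relationships are present in one treatment group and not the" other group. Pathway analysis of the associated features is then read as describing phenotypes linked to e-cig use.
- **Signature.** The features in treatment-specific associations "will be used to predict treatment group, in an effort to produce an e-cig inflammation signature", using several machine-learning methods with ten-fold cross-validation.

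The classes to be predicted are not stated. Nor is it stated whether the two SREC arms are pooled. Elsewhere in item 2 the listed comparisons are all against controls: "We will compare controls to complete substitution with the SREC (with and without nicotine) or NRT". The proteomics paragraph in Protocol section 3 is similar: "the relative abundance of the proteins will be compared in e-cigarette samples versus control samples". SAP item 3 fits pairwise models, but marker by marker. In the analysis sections, SREC against NRT is named in words only for mtDNA features (Protocol 4.g.ii).

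**The concern.** Every participant enters as a smoker. In the SREC arms two exposures change together: aerosol begins, and cigarettes are meant to stop on day 15. With full switching, the label SREC versus continued smoking carries both changes, and the signature model has no cigarette-exposure term to divide them. The NRT arm has the same day 15 quit date and inhales no aerosol, yet nothing ties the signature to that arm or tests it there.

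At stake is the label. If most of the separation comes from removing smoke, NRT quitters would carry the same signature, and a cessation effect would be reported as an e-cig effect. Cross-validation cannot detect this, because a cessation signature predicts SREC versus smoker membership perfectly well in held-out participants.

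**Working it through.** **Inputs from the documents.** 32 per arm and 66% retention (SAP item 1), so 32 × 0.66 = 21.1, or 21 per arm. Two-sided alpha 0.0001 (SAP item 3). CV 0.26 for cell counts and cytokines (Protocol 4.g.ii) and 0.5 for expression and metabolomics (SAP item 3). Hypothesis in Protocol section 2: toxicity falls when e-cigs replace smoking, but "the effect will be less for the e-cig devices compared to quitting with NRT". No cessation or aerosol effect size is given for the signature, so the effects below are assumptions.

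**Step 1: the plan's nearest figure.** The signature step states none. SAP item 3 states 80% power for 1.5-fold (CV 0.26) and 2.1-fold (CV 0.5) differences. Using a two-sample t-test on the log scale with σ = √ln(1 + CV²), σ is 0.256 and 0.472. At 21 per arm the detectable folds are 1.51 and 2.14, which round to the stated values.

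**Step 2: what the example contrast contains.** For the mean level of a marker,

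ln(SREC/smoking) = ln(NRT/smoking) + ln(SREC/NRT).

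The hypothesis puts the left side below zero and the last term above zero, so the cessation term must be the larger in absolute size. The two SREC contrasts then have opposite signs.

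| Assumed NRT/smoking | Assumed SREC/NRT | SREC/smoking | Cessation share of summed absolute log effects |
|---|---|---|---|
| 0.40 | 1.25 | 0.50 | 80% |
| 0.50 | 1.25 | 0.625 | 76% |
| 0.50 | 1.5 | 0.75 | 63% |
| 2/3 | 1.25 | 0.83 | 65% |
| 0.50 | 2.0 | 1.00 | 50% |
| 2/3 | 2.0 | 1.33 | 37% |

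In the first four rows an aerosol effect that raises the marker appears as a decrease against smoking. In the last two it does not.

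**Step 3: illustrative simulation.** 2,000 features (200 cessation-responsive, 200 aerosol-responsive, 100 shared), 21 per arm, CV 0.5. Features are picked by mean difference between SREC and smokers at FDR 0.05, and the resulting score is applied to NRT users.

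| Cessation fall | Aerosol rise | AUC, SREC vs smokers | AUC, NRT vs smokers | Selected features that are cessation-responsive | Selected aerosol-responsive features with negative sign |
|---|---|---|---|---|---|
| 2-fold | 1.25-fold | 1.00 | 1.00 | 91% | 88% |
| 1.5-fold | 1.5-fold | 1.00 | 0.98 | 48% | 0.3% |
| 1.25-fold | 1.5-fold | 0.99 | 0.51 | 13% | 0% |

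The AUC for SREC versus smokers is near 1 in every row, so it says nothing about which exposure drives the score. The NRT column does.

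**Step 4: power of nicotine-SREC versus NRT.** Same t-test, 21 per arm, alpha 0.0001. At CV 0.5: about 1% for 1.25-fold, 9% for 1.5-fold, 66% for 2-fold. At CV 0.26: 9%, 78% and over 99%. These are powers for mean differences; the documents give nothing from which to compute power for the g:t interaction.

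**The case against.** **The contrast is only an example.** A reader might infer that the SAP builds the signature on SREC versus continued smoking. It does not say so: the contrast illustrates the symbol t, and there are four groups to predict. This stands. The gap is an undefined target whose only illustration is confounded.

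**A wrong sign is not shown.** A reader might also infer that the signature will mainly be about cessation and will show e-cigs lowering markers that aerosol raises. Features are selected on g:t interactions, not mean shifts, and a random forest or naïve Bayes score has no raised-or-lowered sign. Steps 2 and 3 concern mean levels and rest on assumed effects. The protocol's remark that "the magnitude of effect is low compared to cigarette smoke" is qualitative toxicology background. Protocol section 3 reports incomplete reversal after quitting: 22 of 34 miRNAs fell, and some methylation changes persist. The preliminary cell counts cannot settle size, because Protocol 4.g.ii describes a decrease of about 2.5-fold while its printed means give 4.03/2.41 = 1.67, an increase with e-cig use. All of this stands.

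**NRT is not a clean comparator.** A reader might take nicotine-SREC minus NRT as the aerosol effect itself. The protocol says the device delivers nicotine at levels similar to cigarettes (section 3, Innovation) and that NRT generally delivers less than smoking (4.f.i). Route differs too, and nicotine is hypothesised to damp aerosol inflammation. Placebo-SREC has no nicotine and is offered varenicline. This stands, and rules out a significant difference from NRT as a condition for calling a feature e-cig-related.

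**Switching is a legitimate aim, and mitigations exist.** SREC versus smoking is a valid estimate of switching and part of the hypothesis; only the label is at issue. Item 3's pairwise models, urinary PG, anatabine, anabasine and nicotelline help elsewhere in the plan, but none is carried into the signature step.

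**Conclusion.** The point holds in limited form. The SAP and protocol leave the signature's classes undefined, and the one contrast they mention combines starting aerosol with stopping cigarettes, with no model term or planned check to separate them. A signature from that contrast may largely reflect cessation if the cessation effect is the larger, which the trial's own hypothesis implies for mean levels. Under assumed effects, the AUC for NRT users versus smokers ranged from 1.00 (2-fold cessation, 1.25-fold aerosol) to 0.51 (1.25-fold cessation, 1.5-fold aerosol). The size is therefore conditional, and it was worked out for mean levels rather than for interaction-selected features. The documents do not establish that the signature will be a cessation signature or will carry the wrong sign. The analysis is exploratory, but the remedy uses data already planned and should be adopted.

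**What to change.** In SAP item 2 and Protocol 4.g.i:

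1. Name the classes to be predicted, and say whether the nicotine and placebo SREC arms are kept apart.
2. Call the SREC-versus-continued-smoking feature set a switching signature.
3. Fit the same g:t model and classifier for nicotine-SREC versus NRT, and show the two contrasts side by side with estimates and intervals.
4. Apply the switching score to NRT participants and report how it classifies them. A score that also separates NRT users from smokers should not be described as e-cig-specific.
5. Do not make a significant nicotine-SREC versus NRT difference a gate. State that this contrast also differs in nicotine dose and route, and that its power for small effects is low (Step 4).
6. Word the proteomics comparison in Protocol section 3 to match.

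The cost is SAP and protocol wording, a little more exploratory analysis on samples already planned, and a less favourable label for the SREC-versus-smoking result. No new participants or assays are needed.

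### The e-cig signature's cross-validated accuracy will be optimistic, because the features, the learner and the minimal feature set are all chosen with treatment labels and no untouched test data remain

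*SAP*

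**What the plan says.** The relevant text is the omics-integration paragraph of SAP item 2, repeated in Protocol section 4.g.i (Data Analysis Plan). The steps come in this order:

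1. Fit m = g + t + g:t for metabolite m and gene, miRNA or cytokine g, where "t is treatment group (e.g., SREC vs. continued smoking"). The filter is significance of the interaction: "A statistically significant g:t interaction p-value would indicate" that the relationship exists in one arm and is absent in the other. No p-value threshold is given.
2. Carry the selected features forward: the miRNAs, genes, cytokines and "metabolites involved in treatment-specific associations will be used to predict treatment group".
3. Try several learners under ten-fold cross-validation (random forests, naive Bayes and lasso are the examples); "the resulting specificity and sensitivity will be assessed to select the best performing model".
4. Assess how much each input contributes, and define the smallest feature set that gives the best cross-validated models.

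The SAP then states that "the cross-validation will help ensure that the predictive models are not overfit and could be predictive on new validation data". Neither document mentions repeating the filter within folds, nested cross-validation, a locked hold-out set, an external cohort or a label-permutation test.

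On multiplicity, the preceding paragraph of SAP item 2 has a general sentence applying Benjamini-Hochberg to the omics analysis. It then defines significance for altered genes and metabolites. It does not name the g:t tests.

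**The concern.** Cross-validation estimates performance fairly only if the held-out subjects played no part in building the model. Here the treatment label enters three times before any accuracy figure exists: in the g:t filter, in the choice of learner and in the choice of minimal set. As the steps are ordered, the filter uses every subject, and the other two choices are made on the result that would serve as the performance estimate. With few subjects and many candidate features, this can make noise look predictive.

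At stake is the credibility of the inflammation signature for e-cigs. Protocol section 4.f.iii (Benefits) intends the study's findings to reach the FDA as policy evidence.

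There is also an error of interpretation. A significant g:t shows that the slopes differ between arms. Both slopes may be non-zero, so it does not show that the association is absent in one arm.

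**Working it through.** **Plan's own figure.** SAP item 1 enrols 32 per arm and says "we will use a conservatively planned 66% retention rate at 5 weeks". 32 × 0.66 = 21.1 and 128 × 0.66 = 84.5, which reproduces its 21 per group and 84 in all. A two-arm classifier, as in the SAP's example, has 2 × 21 = 42 subjects. The documents state no classification accuracy.

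**Set-up (assumptions marked).** Gaussian features with no arm effect, 21 v 21, so true accuracy is 0.50. Each gene-metabolite pair gets a t-test of g:t on 42 − 4 = 38 degrees of freedom, using all 42 subjects. Features from passing pairs enter singly, because the SAP describes its inputs as individual measurements. Stratified ten-fold cross-validation is run with random forest, naive Bayes and L1-logistic regression.

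The documents give no counts for genes or metabolites; the nearest scale is about 5,000 proteins per sample (Protocol section 3). The counts below are therefore assumed. So are the g:t cut-offs: 0.0001, borrowed from the power threshold in SAP item 3, and a nominal 0.05.

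For the minimal-set step, features were ranked by random-forest importance on all 42 subjects, sets of 5, 10, 20 and 40 were tried, and the best cross-validated accuracy was kept. The SAP does not say how contribution will be assessed, so this too is an assumption.

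**Size of the filter.** Expected false pairs = genes × metabolites × cut-off. For example, 2,000 × 500 × 0.0001 = 100 pairs, hence at most about 200 features; the simulation kept 192 on average.

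**Mean accuracy on pure noise:**

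| Genes × metabolites, cut-off | Expected pairs | Mean features kept | g:t filter + best learner | + minimal set | Filter and ranking nested | Runs |
|---|---|---|---|---|---|---|
| 500 × 200, 0.0001 | 10 | 20 | 0.587 | 0.669 | 0.526 | 12 |
| 2,000 × 500, 0.0001 | 100 | 192 | 0.600 | 0.846 | 0.545 | 11 |
| 2,000 × 500, 0.0001, correlated features | 100 | 173 | 0.676 | 0.828 | 0.542 | 13 |
| 2,000 × 500, 0.05 | 50,000 | 2,500 (all) | 0.577 | 0.944 | 0.495 | 9 |
| 5,000 × 1,000, 0.0001 | 500 | 869 | 0.611 | 0.944 | 0.492 | 6 |

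At 2,000 × 500 with independent features, using either p < 0.0001 or the top 20 pairs, the filter plus best learner gave 0.60 to 0.65 (95th percentiles 0.67 to 0.80). Across all settings it was 0.58 to 0.68. With only the top 20 pairs, the minimal-set step gave 0.79. Means carry roughly 1 to 4 points of Monte Carlo error. The nested column fixes the set size at 20 and the learner at naive Bayes, so no best-of-several choice remains in it.

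**Why the two stages differ.** A g:t filter selects on slope differences, not mean differences, so a feature entered singly reveals little about its label. The minimal-set step ranks features on the label directly, and its leak grows with the number of candidates. In the 0.05 row every feature survives the filter, yet the minimal-set step still reaches 0.944.

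**Effect of multiplicity control.** With Benjamini-Hochberg at 5% across all 2,000 × 500 g:t tests, pure noise selected any pair in 5 of 150 trials: 5/150 = 3.3%.

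**The case against.** The strongest reply is that Benjamini-Hochberg already governs g:t. The general sentence in SAP item 2 can be read that way, and SAP item 3 says FDR will be used in practice. On that reading a complete null usually builds no signature at all. This stands, and it rules out the inference that an impressive signature would appear whether or not any signal exists. It also rules out treating about a million false g:t hits as a consequence of the plan. That count needs 20,000 × 1,000 tests at an uncorrected 0.05 (2 × 10^7 × 0.05 = 10^6), and neither the dimensions nor the cut-off is stated for g:t; at 0.0001 the same tests give 2,000. What the reply does not do is make the cross-validation fair. When some pairs do pass, they were still chosen using the held-out subjects' labels.

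A reader might also infer that the g:t filter and best-learner choice alone produce about 90% accuracy from noise. They do not; they give about 60 to 65%. Figures near 90% need the minimal-set step with many candidates, or ingredients the SAP does not state: gene-by-metabolite product terms as inputs (0.99 to 1.00) or a filter on mean differences (0.97).

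Finally, the SAP never says outright that selection uses all samples or that the best cross-validated figure is the one to be reported. Both are inferred from the order of steps and the absence of any other estimate. The SAP also claims only that cross-validation will help, and the signature is a downstream analysis. These points limit the seriousness but do not supply the missing safeguard.

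**Conclusion.** The point holds in this form: followed as written, the pipeline gives an optimistic cross-validated accuracy, which cannot support the SAP's assurance about overfitting. On pure noise at 21 v 21 the apparent accuracy is about 60 to 65% after the g:t filter and learner choice. It is about 67 to 94% once the minimal set is tuned on all samples, against roughly chance (0.49 to 0.55) when filter and ranking are repeated inside training folds.

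These sizes rest on assumed feature counts, Gaussian noise, assumed g:t cut-offs, an assumed importance ranking, a two-arm classifier although the trial has four arms, and 6 to 13 runs per row of the table. The direction of the bias does not depend on those choices. Under enforced Benjamini-Hochberg a complete null rarely yields features, so the missing g:t threshold largely decides whether a noise signature can arise. The misreading of a significant interaction is an error regardless of any simulation.

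The Model 1 comparisons between arms (SAP item 3) are unaffected. The SAP should be changed before the signature analysis is run.

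**What to change.** Amend SAP item 2 and the matching text in Protocol section 4.g.i:

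- Use nested cross-validation. Repeat the g:t screen, the minimal-set search, tuning and the choice of learner within each training fold.
- Report only outer-fold sensitivity, specificity and accuracy, with a label-permutation p-value obtained by rerunning the whole pipeline.
- State that Benjamini-Hochberg applies across all g:t pairs, and at what level, before pathway analysis and prediction.
- Reword a significant g:t to say that the slopes differ between groups, and report group-specific slopes with intervals.
- Remove the sentence on overfitting, or tie it to the outer-fold estimate.

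The cost is SAP and protocol wording plus more computing time. Reported accuracy will be lower, and possibly no signature will emerge. No change to sample size, data collection or Model 1 is needed.
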